##### **Number of insulin injections**

The number of insulin injections will be derived as the average of the reported number on the three days prior to visit 3, 63 and 89. The endpoints will be summarised using descriptive statistics.

##### **Number of weeks off bolus insulin**

The number of weeks the subject is off bolus insulin will be derived based on the question in the CRF "Has the subject stopped taking bolus insulin since last visit". The endpoint will be summarised using descriptive statistics.

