# 8.3.5 Insulin doses

Subjects will be instructed in how to record the insulin doses in the e-diaries. Each record should include date, time point (e.g. before breakfast, before lunch etc.), value, units and type (basal or bolus) of insulin.

Insulin doses will be collected on a daily basis to allow optimal insulin titration.

If a subjects reports an actual bolus insulin dose that deviates from the prescribed bolus insulin dose the subject will be asked to report a reason for this deviation in the e-diary.

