Several subjects have failed to fulfil inclusion criterion 4 due to not fulfilling the requirement of being non-fasting, which may result in a lowering of the subjects C-peptide result. To mitigate this, the measurement of non-fasting C-peptide will be moved to Visit 2 at which the first MMTT is performed. By having the stimulated C-peptide level at Visit 2 during the MMTT above or equal to 0.2 nmol/l the eligible subjects will have the desired beta cell function, and excluding possibly eligible patients, who were fasting at Visit 1, will be avoided.

Termination of bolus insulin use is a good measure of the quality of life of the participating subjects. In order to measure this, an additional secondary endpoint has been introduced in section 4.2.2.1 assessing the number of subjects no longer using bolus insulin. Further, section 5.3.3 has been updated based on this additional endpoint. This end-point should ideally have been

Protocol Amendment 2	Date:	14 March 2016	Novo Nordisk
Trial ID: NN9828-4150	Version:	1.0	
UTN: U1111-1154-7172	Status:	Final	
EudraCT No.: 2014-001215-39	Page:	5 of 27	

implemented from start trial. Data from >200 subjects, will however provide important data from a clinical important parameter.

The INS DNA assay was hypothesized to identify waves of beta-cell death by measuring the ratio of methylated to un-methylated insulin DNA, thus providing a method of assessing beta-cell loss. No functioning assay for analysing differential INS DNA has been developed and it is hence decided to exclude this assessment from the protocol in section 4.2.2.3 and 8.5.1.3.

Treatment with liraglutide and insulin has been clarified in section 5.3.2 and section 5.3.3 with regards to escalation and missed doses.

Maximum number of subjects to be randomised has been deleted in section 1 and section 6.1 to avoid screened failing subjects due to maximum randomisation number met. The period between screening and randomisation is up to 4 weeks and screening in IV/WRS will be monitored very closely when the planned number of randomised subjects is approaching. The current screen failure rate will be considered when the decision of closing screening is taken.

Exclusion criteria 16, 21 and 39 have been updated in section 6.3 for clarification based on questions from participating sites. These changes have no medical or scientific impact on the criteria.

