#### 2.9 Section 5.3.3 Insulin treatment

During the trial subjects will receive insulin treatment in order to achieve metabolic control according to the insulin titration guideline (Appendix A). This insulin treatment will be handled by the local trial sites in collaboration with Novo Nordisk's Insulin Titration Group. *Bolus and/or basal insulin can be stopped or paused at all times during the trial at the discretion of the investigator. The subject's need for bolus insulin will be documented in the eCRF.* It is acceptable to pause or stop insulin treatment if the investigator assesses that the subject is in remission.

**Insulin reduction on the day of liraglutide/ liraglutide placebo initiation and escalation** As it is a blinded trial, wWhen liraglutide/ liraglutide placebo is initiated, the total daily prerandomisation insulin dose should be reduced by 25 % for a minimum of 24 hours after the initiation of liraglutide/ liraglutide placebo.

Thereafter the insulin dose should be adjusted according to the glucose target in Table 5-2. *As it is a blinded trial this insulin reduction applies to all treatment arms.* 

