### 1.1.2.2 Supportive secondary endpoints

#### Supportive secondary efficacy endpoints

- $AUC_{0-4h}$  for MMTT stimulated C-peptide concentration time curve at week 80 relative to baseline\*
- $AUC_{0-2h}$  for MMTT stimulated C-peptide concentration time curve at week 54 and week 80 relative to baseline\*
- Maximum MMTT stimulated C-peptide concentration ( $C_{max, C-peptide}$ ) at week 54 and week 80 relative to baseline\*
- $AUC_{0-4h}$  for MMTT stimulated plasma glucose concentration time curve at week 54 and week 80 relative to baseline
- $AUC_{0-2h}$  for MMTT stimulated plasma glucose concentration time curve at week 54 and week 80 relative to baseline
- Maximum MMTT stimulated plasma glucose concentration ( $C_{max, glucose}$ ) week 54 and week 80 relative to baseline
- Change in total daily insulin dose in units per kg (three day average) from baseline to week 54 and week 80\*
- Change in number of insulin injections per day (three day average) from baseline to week 54 and week 80
- Number of weeks off bolus insulin from baseline to week 54 and week 80
- Change in  $HbA_{1c}$  from baseline to week 54 and week 80\*
- Change in fasting plasma glucose from baseline to week 54 and week 80\*
- Change in fasting C-peptide from baseline to week 54 and week 80\*
- Change in fasting glucagon from baseline to week 54 and week 80
- 7-point self-measured plasma glucose (SMPG) profiles. The following endpoints will be derived:

- 7-point profiles at week 54 and week 80
- Change in postprandial glucose (PPG)/prandial increment (breakfast, lunch, dinner and average over the three meals) from baseline to week 54 and week 80
- Change in mean of 7-point profiles from baseline to week 54 and week 80
- Before breakfast SMPG at week 54 and week 80
- Change in patient reported outcome (PRO) scores (SF36, Experience of Treatment Benefits and Barriers, Diabetes Treatment Satisfaction Questionnaire (DTSQ)) from baseline to week 54 and week 80

\* Key supportive secondary endpoint prospectively selected for disclosure (e.g. clinicaltrials.gov and EudraCT)

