  - The endpoints will be analysed using normal linear regression model for the endpoint with treatment, stratum and sex as fixed factors and age and baseline value as covariates. Treatment means (LSMeans) and treatment differences will be presented with 95% CIs. The analysis will not account for missing data. The number of insulin injections will be derived as the average of the reported number on the three days prior to visit 3, 63 and 89.
- As only the insulin doses prior to visit 3, 63 and 89 will be transferred from the eDiary, the calculation of the endpoint “The number of weeks the subject is off bolus insulin” is not derived based on the dose information in the eDiary as originally planned, but based on the question in the CRF “Has the subject stopped taking bolus insulin since last visit”.
- The following analysis has been deleted in alignment with standard in GLP-1 trials:
  - A normal linear mixed effect model will be fitted to the 7-point SMPG profile data at week 54. The model will include treatment, time-point, the interaction between treatment and time-point, sex and stratum as fixed factors, age as a covariate and subject as a random effect. The variance-covariance matrix will be unstructured and may depend on treatment if an assumption of equal variance-covariance matrix between treatments turn out not to be reasonable. From this model the treatment

differences at each time-point will be estimated and explored. The same analysis will be made using the 7-point SMPG profile data at week 80

- For the analysis of within-subject variability of the before breakfast SMPG, it has been deleted that the 95% CI will be calculated using the delta method. Furthermore it has been clarified that the analysis will not account for missing data.
- As eGFR is only assessed at visit 1, 63 and 89, the statistical analysis has been changed from a MMRM to a normal regression model. Furthermore, it has been specified that the analysis will be done for the log-transformed endpoint:
  - The eGFR endpoint will be log-transformed and analysed using normal linear regression model with treatment, stratum and sex as fixed factors and age and baseline value as covariates. Treatment means (LSMeans) and treatment ratio for the back-transformed results will be presented with 95% CIs. The analysis will not account for missing data.
- Added:

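### Weeks off bolus insulin is derived from a question that asks only about stopping, so it can be miscounted for subjects who resume bolus or are already off it at baseline; the daily e-diary is a better source

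*SAP*

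**What the plan says.** SAP section 1.1.2.2 lists the supportive secondary efficacy endpoint as "Number of weeks off bolus insulin from baseline to week 54 and week 80". The rule is in SAP 2.4.1.1, under the heading for this endpoint: "The number of weeks the subject is off bolus insulin will be derived based on the question in the CRF", and the question is "Has the subject stopped taking bolus insulin since last visit". The result is only summarised descriptively. Nothing is said about restarts, part weeks, withdrawal or status at baseline.

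SAP section 3 discloses that the endpoint "is not derived based on the dose information in the eDiary as originally planned". The reason given is that, under the data handling plan, only doses before visits 3, 63 and 89 are transferred from the e-diary.

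The endpoint came in with Protocol Amendment 2 (14 March 2016). Its section 2.9, which revises Protocol 5.3.3, states that "Bolus and/or basal insulin can be stopped or paused at all times during the trial at the discretion of the investigator" and adds that need for bolus insulin is recorded in the eCRF. Its introduction concedes that the endpoint should have been there from the beginning, and continues: "Data from >200 subjects, will however provide important data from a clinical important parameter".

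On the e-diary, Protocol 8.3.5 says "Insulin doses will be collected on a daily basis to allow optimal insulin titration", with each record labelled basal or bolus. Protocol 8.6.3 issues the e-diary to every subject at Visit 2.

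**The concern.** The endpoint is a duration, so it needs to know when a subject was off bolus and when back on. The question as worded captures only the first transition. After a *yes*, a later *no* fits both a subject who is still off and one who has resumed. A subject already off bolus at baseline never makes the transition that the question asks about. The SAP does not say how any of these cases is turned into weeks, so two programmers could follow it faithfully and reach different values.

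At stake is the arm-by-arm description of an endpoint that the sponsor introduced as a measure of quality of life. If resumption or baseline status differs between arms, the summary could mislead about which arm spent more time without mealtime insulin.

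**Working it through.** The plan gives no sample size, power or expected value for this endpoint, so there is no figure to reproduce. The check compares the rule with the histories that the protocol allows, and then looks at coverage.

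**Histories the protocol allows**

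- Stop and restart: Amendment 2 section 2.9 permits pauses at any time.
- Off bolus at entry: inclusion criterion 7 (Protocol 6.2) accepts subjects who are not insulin dependent if they are in remission.
- Stop once and stay off.

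**Effect on the count**

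The weeks below are hypothetical. The SAP does not say how a *yes* becomes a number of weeks, so I assume that a recorded stop is carried forward to the end of the window.

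- True weeks = (restart week, or end of window if none) − (stop week).
- Counted weeks = (end of window) − (stop week), or 0 if no stop is ever reported.

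| History | True, to week 54 | Counted | Error | True, to week 80 | Counted | Error |
|---|---|---|---|---|---|---|
| Stop 10, restart 16 | 16 − 10 = 6 | 54 − 10 = 44 | +38 | 6 | 80 − 10 = 70 | +64 |
| Stop 10, restart 40 | 40 − 10 = 30 | 44 | +14 | 30 | 70 | +40 |
| Off from baseline, no new stop | 54 | 0 | −54 | 80 | 0 | −80 |
| Stop 10, no restart | 44 | 44 | 0 | 70 | 70 | 0 |

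The error can be positive or negative. It is zero for a subject who stops once, after the question was introduced, and does not resume.

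**Coverage of the question**

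- Planned number randomised: 304 (Protocol 6.1).
- Expected by Amendment 2 to contribute data: more than 200.
- Remainder: fewer than 304 − 200 = 104. Since 104/304 = 34.2%, this is at most 103 subjects, or 103/304 = 33.9%.

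This takes the remainder to be the subjects enrolled before the amendment. The documents do not give enrolment at that date, so it is a ceiling and not a count. These subjects lack answers for the period before the amendment; nothing suggests that they could not answer afterwards.

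**The alternative source**

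- Dose records are daily and typed (Protocol 8.3.5), for all subjects from Visit 2 (8.6.3).
- Entries pass automatically from the device to a database (Protocol 13.3).
- Daily doses are to reach the sponsor's titration group within 24 hours of each contact on weekdays (Appendix A, section 4).

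The records are thus planned for the whole trial and already reach the sponsor. The only reason given for not using them is the scope of the transfer to the analysis data.

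**The case against.** The strongest reply is that the CRF itself is not in the documents. Amendment 2 describes the eCRF item as the need for bolus insulin, which is wider than stopping. Concomitant medication records carry start and stop dates (Protocol 8.2.2), and Amendment 2 section 2.19 puts insulin at Visit 1 and brand changes on that form. Restarts may therefore be recorded somewhere. This stands as a limit on what can be claimed, but it does not rescue the rule, because the SAP derivation does not use those fields.

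Second, the e-diary is imperfect. A day without a bolus entry may be a day without a dose or a day without an entry. Protocol 8.4.2.7 foresees missing diary data, and Amendment 5 section 2.10 foresees retraining for poor diary completion. This stands, and it is why the fix needs a completeness rule. Nor is there a worked-out e-diary algorithm to go back to: only SAP section 3 calls the e-diary the planned source, and Amendment 2 section 2.40 specifies only a descriptive summary.

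Third, the SAP discloses the switch and its reason, among changes made before the code break. The endpoint is not among the starred key secondary endpoints and carries no test. The starred insulin endpoint, change in total daily dose, does not depend on this question. All of this limits the consequence.

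A reader might also infer that the missing early months are when stopping is most likely. The documents do not say so, and that argument should not be used.

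**Conclusion.** The point holds as a weakness in the derivation. Weeks off bolus cannot be derived reliably from the stated question alone, and can be miscounted in either direction for subjects who resume bolus or are off it at baseline. The illustrative errors run from −54 to +38 weeks at week 54, and from −80 to +64 at week 80. They rest on assumed histories and on carrying a stop forward. The number of subjects affected and the net direction by arm are unknown.

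Three stronger readings are tempting, and the documents do not support them. That the endpoint will be wrong for every contributor fails because a single lasting stop is counted correctly under carry-forward. That restarts go unrecorded cannot be established without the CRF. That a third of the trial has no data overstates the coverage gap: fewer than 104 subjects lack answers, and only for the period before Amendment 2.

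Since the endpoint is supportive and descriptive, the trial's main conclusions are not touched. The change is still worth making, because a better source is already planned for all subjects.

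**What to change.** Extend the e-diary transfer to all records of type bolus for weeks 0 to 80. Define the endpoint as the number of weeks with no bolus dose recorded. Pre-specify a minimum number of completed diary days for a week to be evaluable, since a missing entry does not prove that no dose was taken. Report evaluable weeks by arm, and keep the CRF question as a cross-check.

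If the transfer cannot be extended, state in the SAP, before the code break, which CRF fields give the stop and restart dates. Also state how baseline-off subjects, part weeks, withdrawals and subjects enrolled before Amendment 2 are handled.

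The cost is a larger e-diary extract and a paragraph of SAP text, with no new data collection. The downside is that some weeks will not be evaluable where diaries are incomplete.

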### **HbA1c, FPG, fasting C-peptide and fasting glucagon**

The HbA1c and FPG endpoints will be analysed using a similar model as described for the primary endpoint except that the corresponding value at baseline will be included as a covariate and the analysis will be made on the original scale (i.e. without the log-transformation). Consequently, treatment means (LSMeans) and treatment differences will be presented with 95% CIs.

The fasting C-peptide and fasting glucagon endpoints will be analysed using a similar model as described for the primary endpoint except that the corresponding value at baseline will be included as a covariate. The values will be log-transformed prior to analysis, i.e. the change will be calculated for the log-transformed data and the log-transformed value at baseline will be included as a covariate.

In addition to the endpoints listed in Section [1.1.2.1](#), the following binary endpoints are derived for all subjects at baseline, week 54 and week 80:

- Hba1c < 7.0 %.
- Hba1c <= 6.5 %.

All the endpoints will be summarised using descriptive statistics and presented graphically.

### **Self-measured plasma glucose profiles**

The 7-point SMPG profile will include a pre-meal measurement and a measurements 90 minutes after start of meal for breakfast lunch and dinner as well a measurement at bedtime.

The 4-point SMPG profile will be used for titration of the insulin dose and will include a pre-meal measurement for breakfast, lunch and dinner and a measurement at bedtime.

#### ***7-point SMPG profiles at week 54 and week 80***

The 7-point SMPG profiles will be summarised using descriptive statistics and presented graphically.

#### ***Change in prandial increment and change in mean of 7-point SMPG profile***

The prandial increment at a meal will be calculated as the post-meal measurement minus the pre-meal measurement. The prandial increment will be calculated for breakfast, lunch and dinner separately. The average over the three meals will also be calculated. The mean of the 7-point SMPG profile will be calculated as the mean of all 7 points.

The endpoints will be analysed using a similar model as described for the primary endpoint except that the corresponding value at baseline will be included as a covariate and the analysis will be

made on the original scale. Consequently, treatment means (LSMeans) and treatment differences will be presented with 95% CIs.

The endpoints will be summarised using descriptive statistics and presented graphically.

### ***Before breakfast SMPG***

The within-subject variability will be evaluated using the before breakfast measurements from 4-point SMPG profiles at week 54 and week 80.

A normal linear mixed effect model will be fitted to the before breakfast SMPG values at week 54. The model will include treatment, sex and stratum as fixed factors, age as a covariate and subject as a random effect. The model will assume independent within- and between-subject error variances depending on treatment. The within-subject variance will be presented for each treatment with the 95% CI. The analysis will not account for missing data.

The same analysis will be made for the before breakfast SMPG values at week 80.

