## **1** Introduction including rationale for the protocol amendment

This amendment was prepared to update Protocol NN9828-4150 version 6.0 dated 08 November 2016 with the following changes:

- To allow for the use of Continuous Glucose Monitoring (CGM) and Flash Glucose Monitoring devices for patients having access to these. Allowing the use of these devices will ease the burden for the patients during their trial participation. All end point related data are still to be measured using the BG meter provided by Novo Nordisk and it is hence assessed that neither patient safety nor data integrity is affected by introducing the two device options.
- Visit 4 (V4), in the flowchart for section 2.2 Visit 1 to 37 procedures once 80 subjects have been randomised, was removed in Global Protocol Amendment No. 2 due to removal of PK sampling at this visit. As this visit also serves the purpose of monitoring the patient after initiation of liraglutide/ liraglutide placebo, V4 is re-instated as a phone contact and with safety monitoring only.
- In section 2, the flowchart has been updated to reflect the re-introduction of V4 once 80 patients have been randomised. Furthermore, the tick mark for IV/IWRS call for visit 89 and the drug accountability for visit 3 are removed as these are not applicable. In addition, monthly mandatory urine pregnancy test for female Polish subjects has been incorporated due to a local requirement.
- In section 5.3.4, the period for which systemically corticosteroids, monoamine oxidase (MAO) inhibitors, systemic non-selective beta-blockers and growth hormone as well as treatment with any medication for the indication of diabetes or obesity other than insulin and trial medication is prohibited has been extended to include the follow-up period (week 54 to week 80). Patients may not initiate these medications at any time during the trial period as secondary efficacy parameters may be influenced.
- In section 6.3, contraceptive requirements for Poland have been added. In addition, clarifying editorial changes has been made to the UK requirement for males of reproductive age.
- In section 6.6, it has been clarified that vaccines taken during the follow-up period will not lead to exclusion from the trial as no trial medication is administered. Vaccines are, however, still prohibited medication during the entire trial period.
- In section 8.3.2, the option of using CGM and Flash Glucose Monitoring devices has been introduced.

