## 2.7 Section 8.3.2 Self-measured blood glucose

Subjects will be instructed in how to record the results of the self-measured blood glucose (SMBGs) in the e-diaries. The record of each SMPG will include date, time point (e.g. before breakfast, before lunch, etc.) and value. BG should always be measured when a hypo- or hyperglycaemic episode is suspected. Hypoglycaemic and hyperglycaemic episodes will be recorded by the subject in the e-diary (see Section 8.6.3). The investigator may ask the subject to perform additional SMPG measurements if needed for any safety reason.

If subjects have their own CGM or Flash Glucose Monitoring devices they may use these for measuring the 4-point profiles only (i.e. before breakfast, before lunch, before dinner and bedtime) as per section 8.3.3 The use of these devices must be recorded in EDC.

The instruction of use of the CGM and Flash Glucose Monitoring devices is at the discretion of the investigator. These devices will not be supplied nor compensated by Novo Nordisk.

All subjects must receive and be instructed in the use of the blood glucose meter provided by Novo Nordisk. This Novo Nordisk supplied blood glucose meter must be used to:

- confirm any glucose values measured in connection with a hypoglycaemic episode
  - $\circ \leq 3.9 \text{ mmol/l} (70 \text{ mg/dl}) \text{ or}$
  - $\circ$  > 3.9 mmol /l (70 mg/dl) occurring in conjunction with hypoglycaemic symptoms
- confirm any glucose values measured in connection with a hyperglycaemic episode

   > 16.7 mmol/l (300 mg/dl)
- measure all 7-point profiles (all 7 SMPGs from the same device)

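### Before-breakfast SMPG variability is taken from 4-point profiles that subjects' own CGM or flash devices may supply, although Amendment 5 says endpoint data stay on the supplied meter

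*SAP*

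**What the plan says.** The introduction to Protocol Amendment 5 justifies admitting personal glucose sensors on this ground: "All end point related data are still to be measured using the BG meter provided by Novo Nordisk". From that it concludes that data integrity is unaffected. The operative text, Amendment 5 section 2.7 (protocol 8.3.2), reads: "If subjects have their own CGM or Flash Glucose Monitoring devices they may use these for measuring the 4-point profiles only". It lists the before-breakfast point among those covered, and adds: "The use of these devices must be recorded in EDC". The supplied meter is mandatory for three purposes only: to "confirm any glucose values measured in connection with a hypoglycaemic episode", to "confirm any glucose values measured in connection with a hyperglycaemic episode", and to "measure all 7-point profiles (all 7 SMPGs from the same device".

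The endpoint lists (protocol 4.2.2.1, SAP 1.1.2.2) carry "Before breakfast SMPG at week 54 and week 80" without the asterisk that marks key endpoints. They do not name the source profile, and the item follows the 7-point heading. The analysis sections do name it. Protocol 17.4.1.1 and SAP 2.4.1.1 both say: "The within-subject variability will be evaluated using the before breakfast measurements from 4-point SMPG profiles at week 54 and week 80". The model has treatment, sex, stratum, age and a random subject effect, with variances by treatment. It has no device term.

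Amendment 2 section 2.24 (protocol 8.3.4) adds that on a day with a 7-point profile, preferably the day before the visit, those values replace the 4-point values.

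**The concern.** The quantity reported here is a variance. Imprecision in the instrument adds to it directly and does not average out as it might for a mean. If some of a subject's mornings are measured on the meter and others on a sensor, a stable offset between the two also counts as variability within the subject. The per-arm figure would then combine glycaemic variability with measurement differences.

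SAP 1.3 states that the plan rests on the protocol including Amendment 5. SAP section 3 lists changes to this very analysis (the delta-method interval was dropped and missing data were clarified). Neither place restricts the analysis to meter readings or adds a device sensitivity analysis. What is at stake is the meaning of two sets of per-arm variances, at weeks 54 and 80.

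**Working it through.** **Tracing the data source.**

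1. The analysis text takes before-breakfast values from 4-point profiles.
2. Amendment 5 permits own devices for 4-point profiles, the before-breakfast point included.
3. The supplied meter covers 7-point days and confirmation of hypo- and hyperglycaemic values. A within-subject variance needs several days, so ordinary readings on other days may come from a sensor.
4. Amendment 5 does not say whether a confirming meter value replaces the sensor value in the profile, so both cases are computed below.

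The plan gives no figure to reproduce here: device share, device accuracy and readings per subject are not stated.

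**Assumed inputs (none from the documents).** Mean glucose 7 mmol/l; meter CV 5%; sensor CV 3%, 5%, 10% or 15%; stable offset d between -1 and +1 mmol/l; true within-subject SD 1.5 or 2.0 mmol/l; n = 3 or 7 readings, of which k are on the meter (k = 0 to n-1).

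**Sensor values stay in the profile.** With v = SD² + (CV × 7)² for each instrument,

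E[S²] = (k·v_m + (n-k)·v_s)/n + d²·k(n-k)/(n(n-1)), divided by v_m.

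- Lowest: SD 1.5, sensor CV 3%, d = 0, k = 0. (2.25 + 0.0441)/(2.25 + 0.1225) = 2.2941/2.3725 = 0.967.
- Highest: SD 1.5, sensor CV 15%, |d| = 1, n = 3, k = 1. v_s = 2.25 + 1.1025 = 3.3525. (2.3725 + 2 × 3.3525)/3 + 2/6 = 3.0258 + 0.3333 = 3.3592, and 3.3592/2.3725 = 1.416.

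A device user's variance therefore changes by about -3% to +42%.

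**Confirming meter values replace sensor values.** I simulated 150,000 subjects per setting and replaced sensor readings ≤3.9 or >16.7 mmol/l by the meter value.

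- Lowest: SD 2.0, sensor CV 3%, d = -1. With k = 0 the ratio is about 0.78 to 0.79 (about -21%); with k = 1 and n = 7 it is about 0.84.
- Highest: SD 1.5, sensor CV 15%, d = +1, n = 3, k = 1, ratio about 1.40 to 1.41 (about +41%).
- With no offset, 2.0% to 8.5% of sensor readings would trigger a confirmation.

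**Shift for a whole arm.** If 20% of subjects use a device, the shift is 0.2 × (ratio - 1). 0.2 × (-0.21) is about -4%, and 0.2 × 0.416 is about +8%.

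**Sampling error for comparison.** With 60 completers per arm (the planning figure in SAP 2.1), 3 readings give 60 × 2 = 120 df and 7 readings give 60 × 6 = 360 df. The chi-square 95% limits for a variance are 0.788 to 1.310 and 0.869 to 1.164 times the estimate, i.e. -21% to +31% and -13% to +16%.

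**If device use differed between arms.** Let r be the device-to-meter variance ratio, assumed 0.7 to 1.5, with 10% users in one arm and 30% in another. The ratio of arm variances is (0.7 + 0.3r)/(0.9 + 0.1r). This is 0.91/0.97 = 0.94 at r = 0.7 and 1.15/1.05 = 1.10 at r = 1.5. The documents do not indicate any such imbalance.

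**The case against.** **The endpoint may be meant as a 7-point endpoint.** In both endpoint lists the item follows the 7-point heading, and 7-point profiles stay on the supplied meter. If it belongs there, the Amendment 5 rationale would be consistent with the lists. This stands as an ambiguity in the lists. It does not remove the conflict, because both analysis sections name the 4-point profiles explicitly.

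**Meter values are already present near the visit.** On 7-point days the meter values replace the 4-point values, and 7-point profiles are scheduled at Visits 63 and 89. At least one meter reading per time point is therefore likely. That is also what makes mixed instruments within a device user likely, since the remaining days may be sensor days.

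**Existing safeguards.** SAP 2.2 provides a data review before lock using a fake randomisation and optional sensitivity analyses. SAP section 2 allows supplementary analyses. These are discretionary and not specific to devices. A reader might also infer that a week-80 device decision would be made unseen after the sponsor is unblinded at the interim lock. The documents do not support that: SAP 2.2 requires exclusions to be documented before the full lock, and any decision taken after code break to be clearly stated.

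**Unseen sources.** The EDC form and the data handling plan cited in SAP section 3 are not available. They may identify the device by reading or select the days. This stands, and it is why the fix has two variants.

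**Small consequence.** The endpoint is non-key, and the illustrative arm shift lies inside sampling error. This also stands, and it limits the weight of the point.

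**Conclusion.** The statement that all endpoint-related data remain on the supplied meter does not hold for the before-breakfast within-subject variance at weeks 54 and 80. For subjects using their own device, the variance may include sensor error and a meter-to-sensor offset. No planned analysis separates these.

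Both user-level ranges include zero and rest wholly on assumed device characteristics. The arm-level shift also assumes 20% use. The true size and direction are unknown.

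A reader might infer a bias between arms, or doubt the trial's glycaemic results more widely. The documents support neither. Nothing shows that device use differs by arm, and the SAP presents per-arm variances for this endpoint. The primary, key secondary and 7-point endpoints are not derived from these profiles, and hypo- and hyperglycaemic values must be confirmed on the supplied meter. This is a minor point that is worth settling because it is cheap to settle.

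**What to change.** **Preferred, where still feasible.** State in protocol 8.3.2 that the before-breakfast readings used at Visits 63 and 89 are taken on the supplied meter, and name the days. The cost is a few extra finger-sticks around two visits, which partly reverses the burden relief that Amendment 5 sought.

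**Otherwise, before the interim lock.** In SAP 2.4.1.1, prespecify for both time points a sensitivity analysis of the within-subject variance:

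- If EDC identifies the device by reading or by period, limit the analysis to supplied-meter readings.
- If not, exclude subjects recorded as device users.
- In either case, report the number of users by arm.

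This takes one or two sentences and leaves the main analysis as planned. The cost is some lost readings or subjects; a user left with a single meter reading adds no within-subject information. Excluding users also conditions on device use that can begin after randomisation. The result is therefore a check on the per-arm variances and not a randomised comparison. Fixing the rule now makes a later week-80 decision unnecessary.

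Correcting the sentence in the Amendment 5 rationale is housekeeping only, since protocol 8.3.2 is the operative text.
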